### **C. Description, Risks and Justification of Procedures and Data Collection Tools:**

This study involves only psychiatric interviews, well validated, commonly used rating scales, computer-based cognitive tasks that do not involve deception or distressing the participant, and a noninvasive procedure (magnetic resonance imaging scans without sedation or contrast). Thus, this study does not involve any risks greater than routine risks of a routine physical or psychological examination. This study was developed in consultation with NIMH Program to adhere to the NIMH roadmap for investigating novel therapeutics (NIMH Strategic Plan 3.1). It may benefit participants by providing a more comprehensive psychiatric assessment to them than usual care. It may benefit society in that the study has a high likelihood of providing novel information critical to the development of a nonpharmacologic treatment for a serious psychiatric condition. Overall, the risk/benefit ratio favors societal and individual benefits.

Study assessment procedures include behavioral testing and MRI scanning. These will take place over the course of two weeks with two on-site visits. Common risks include loss of school time and increased psychological stress as a result of participation. We have found that the proposed study period has been well-tolerated by child psychiatric outpatients. During the assessment days, participants will be given as many breaks as needed between to reduce fatigue and ensure adequate effort/concentration. To minimize loss of school time (or parental work commitments), some evening and weekend assessment times will be offered. Participants will also be able to complete assessments at times most convenient for them including days off from school, holiday breaks and summer vacation. In addition, this protocol incorporates online assessment where possible to reduce loss of personal/occupational/school time.

With regards to clinical assessments, there are minimal risks associated with completion of cognitive tests (WASI-II) or rating scales. Children may experience some frustration if they lose points during cognitive testing. They also may also become bored with some of the procedures. Furthermore, some questions during the clinical interview or completion of parent/self-report rating scales may be deemed "personal" in nature; therefore, adolescents and their parents will be informed that they do not have to answer any questions they do not feel comfortable answering. Adolescents may divulge information suggesting that they are in danger, requiring urgent psychiatric care or reporting to authorities.

Drs. [name] or [name] will supervise all clinical portions and respond to urgent psychiatric issues per standard of care. Caregiver concerns on follow up phone call will be evaluated by Drs. [name] or [name] immediately. Any online forms will be reviewed by Drs. [name] or [name] within three business days of receipt. Should any information arise suggesting the adolescent is in danger to self, others, or psychiatrically disabled, Drs. [name] or [name] will immediately be contacted to establish safety and coordinate appropriate care. Drs. [name] or [name] will be contacted for any suspected child abuse and neglect; they will coordinate reporting and safety maintenance as mandated by law. [name], the PI, will always be contacted via pager in the event of any suspected safety concern, urgent, or emergent clinical issue.

Procedures and timing for reportable events will be as defined by current applicable COMIRB policies (specifically, Safety Report Policy, Continuing Review Policy, and Unanticipated Problem Reporting Policy located here: <https://www.ucdenver.edu/research/comirb/policies>) and NIMH Reportable Events Policy. Reportable events discovered by study personnel will be to [name] immediately upon discovery via pager. Any such event will be reported to COMIRB according to COMIRB Safety Report Policy. Reporting by the PI, COMIRB, and ISM to the NIMH PO will comply with the NIMH Reportable Events Policy.

Regarding completion of behavioral tasks, it is likely that adolescents will become mildly frustrated or annoyed when completing certain behavioral tasks. During these tasks, adolescent mood will be monitored to ensure that

the adolescent does not become overly frustrated. Prior use of these tasks has shown that children with clinically significant irritability are generally able to complete these tasks without difficulty or significant negative affect.

With regards to fMRI, some children may become nervous or uncomfortable during MRI scanning. High noise environment is a risk of fMRI and all adolescents are required to wear ear protection. All adolescents are warned of unusual sensations during fMRI which are possible due to nerve stimulation. Standard MRI metal screens and MRI-safe gowns will be employed to ensure no ferromagnetic or electronic material will be brought in by the participant into the scanner. A number of procedures have been established to reduce the discomfort of adolescents during neuroimaging protocols (see Protection Against Risks below). As with all Brain Imaging Center protocols, every effort will be made by Brain Imaging Center personnel to engage adolescents by creating a pleasant and positive atmosphere. In the event that a child cannot complete the assessment in the allotted time, an additional day of testing may be scheduled if agreed to by the child and parent/guardian.

Consistent with Brain Imaging Center protocol, a urine pregnancy test will be given to adolescent females to prevent incidental research MRI scan of pregnant subjects. Pregnancy is an exclusion criterion for the study and this will be discussed during the informed consent process. Families will be notified that positive pregnancy screening results will be disclosed to the adolescent only to conform with the Colorado minor consent and confidentiality law. Pregnant adolescents will be excluded from all arms of the study, due to the high likelihood that a positive test will result in acute distress that may confound the study due to a systematic assignment of distressed, pregnant adolescents to the non-MRI arm. Consultation of a positive result will be with a licensed clinician on call for the scan to provide consultation on the interpretation of a positive urine pregnancy screen, rights, and referrals. Pregnant females may re-enroll when they are no longer pregnant.

There are a number of potential risks associated with use of MRI scanning procedures which we will also seek to minimize. First, the magnet within the scanner can cause electric devices including pacemakers, beepers, and watches to malfunction, and some magnetic items can be pulled into the magnet. Therefore, in line with Brain Imaging Research Center requirements, all MRI participants will complete a questionnaire regarding the presence of metal/ electronic devices. Prior to scanning, this questionnaire will be reviewed in detail with the adolescent and their parents to ensure that the adolescent does not have any metal on or in his/her body, and we will ask him/her to take off any metal objects he/she may be wearing (such as a watch or jewelry). Adolescents with implanted electrical devices or ferromagnetic foreign bodies in critical soft tissues will be excluded from the MRI portion of this study. Another risk is the high noise-level of an operating MRI machine. Thus, all MRI participants will be required to wear ear protection.

Another risk associated with MRI scanning is anxiety or discomfort related to being inside the magnet bore. For those individuals who have concerns about the MRI examination, are anxious about the procedure, or simply have difficulty lying still, behavior modification is offered. The MRI-simulator ("mock scanner") at the Brain Imaging Research Center (BIC) allows for acclimation to MR protocols, improves comfort, and decreases potential anxiety. All children will complete a mock scan prior to actual MRI scanning. Further, to reduce anxiety, a professionally edited videotape of a child having an MRI is available for viewing, and the adolescents and their families may also see the MRI scanner in advance. Parents may also watch their child in the scanning room during MRI procedures via video monitoring if desired. Due to the COVID-19 pandemic, the BIC may restrict access to the mock scanner. A real-scanner acclimation procedure will be used in the event that the mock scanner is not available. The information in the mock scanner protocol will be reviewed with the participants, which includes images of the mock scanner. Additionally, the actual MRI scanner will be shown to subjects prior to scanning for comparison. Real-scanner acclimation to the noise will occur over 8 minutes during the short calibration sequences and longer structural scans prior to the task. Total time for acclimation in the real scanner is the same as for the mock scanner. Scanning sessions will be terminated immediately upon the request of the adolescent, or if the adolescent becomes upset by the noise, claustrophobia, anxiety or poor performance during testing.

No sedation is used. The on-call clinician will also consult with any adolescent participant who becomes distressed through the course of MRI acquisition, or any other portion of the study. For imaging, participants will be notified during the informed consent process that their neuroimages will not be clinically read by a radiologist or other qualified physician. Regardless, [name] or [name] will immediately be notified of suspicion of any neuroimaging anomaly detected by study personnel. A licensed clinician will review suspected anomaly. If the clinician shares suspicion or cannot explain the anomaly as non-significant, e.g. a common imaging artifact, the

clinician on call will report it to the adolescent's parents or guardian and provide them a copy of their image for their practitioner to review.

Monitoring and responding to adverse events is primarily the responsibility of [name], the PI, a board-certified child psychiatrist with COMIRB oversight. An Independent Safety Monitor (ISM) will be responsible for an annual review of adverse events and will be notified unanticipated problems or adverse events. [name], has agreed to the ISM role. He is a board-certified child psychiatrist and an expert in cognitive trials involving youth with affective and disruptive behavioral disorders. [name] meets financial and professional independence criteria from all members of the study team as described by the NIMH Policy Governing the Monitoring of Clinical Trials.

The ISM, [name], will be immediately notified of any serious adverse event. In addition, once yearly, he will receive data on accrual, all reportable events, and post-IBT mood scale scores for all treatment arms for a cumulative assessment of study safety. [name] will be granted access for any inquiry about data quality and management. Based on this information he will send a letter to the NIMH PO recommending the suspension, termination, or continuation of the study.

All study assessment information will be considered confidential. Data will be stored in locked-file cabinets at CU behind a locked door. Participant data will be stored using subject identification numbers only to reduce breaches in confidentiality. Identification numbers will code data entered for computer analysis, and the data coordinator will keep all names and code numbers. Findings will be made available to legitimate agents of the adolescents (parents, schools, treating psychologists, physicians), and only with the express, written consent of the parents/guardians. All publications and presentations will report on deidentified data.

#### Criteria for Stopping

If more than 75% of enrollees allotted to any treatment arm do not complete the protocol, the PI will review the feasibility of that arm with the ISM. The study will be stopped if there is any Serious Adverse Event related to the research. The PI, ISM, COMIRB, and NIMH will determine if changes are needed for the research to continue or if it will be closed.

#### **E. Potential Scientific Problems:**

This study is designed to assess the targets of IBT for the treatment of clinically significant irritability in patients, i.e. we are testing the association between the targets and severity of irritability within clinically irritable patients. This study does not include a group of non-irritable patients. The mechanism of IBT's effect on irritability is unknown. While the training is designed to target hostile interpretation bias via reinforcement learning, the training may work through alternative means. For example, youths with severe, chronic irritability have deficits in labeling face-emotions. The training may work through increasing emotion recognition; such training has been proposed to treat irritability. In this case, this study will generate measures of reliability and neural response for future investigations. Indeed, procedures for exploratory Aim 3 will gather preliminary evidence of efficacy.

#### **F. Data Analysis Plan:**

Development of Computational Models. The application of computational models of learning to behavior and neural response is integral to both the training and scientific aims of this proposal. We will apply well-established models of human reinforcement learning (variants of Rescorla-Wagner and Pierce-Hall that incorporate stimulus generalization) and assess their fit to IBT data. Goodness of fit will be assessed with expectation-maximization and maximum-likelihood algorithms. Models will also be tested in secondary analyses of IBT data of youths with DMDD from [name] lab. The parameters for the model will be (a) parameters determining initial value, i.e. probability of angry, for each stimulus, (b) learning rate, (c) a parameter determining degree of generalization among stimuli, (d) reliability of judgments (inverse choice temperature). Simulation of the model under parameters estimated from the data will yield predictions for the trialwise likelihood that each face is considered angry and of the trialwise prediction error. (Note: these last two variables could be used as predictors in the fMRI analysis.) For transparency, analytic code (not any data) for all models will be posted to online software development repositories.

Hypothesis Testing. To maintain rigor, all analyses will involve omnibus models with appropriate diagnostics for model fit and influential data. Minimization procedures should ensure balance on the environmental and biological factors (sex, age, SES, and IQ) that may influence hypothesized associations. Additional potential factors are anxiety, depression, pubertal development, and in- or out-of-scanner training. The effects of all of these factors on independent variables will be assessed. If an imbalance across training groups occurs in any of these factors or a significant association is detected between these factors and an independent variable, it will be entered into the omnibus model as a covariate.

Hypothesis 1.1: Baseline hostile interpretation bias is associated with baseline irritability. Linear regression with pre-training balance point (interpretation bias) as a dependent variable and pre-training ARI (irritability) as an independent variable.

Hypothesis 1.2: Active but not sham, IBT will reduce hostile interpretation bias. Mixed-effects linear regression with balance point (interpretation bias) as a dependent variable and training condition (active vs. sham), and time of interpretation bias assessment (pre- or post-training) as independent variables of interest and person as a grouping variable and random effect. Similar models will test for group differences in active or sham IBT on other measures of hostile interpretation bias after training.

Hypothesis 2.1: The rate of learning new associations to ambiguous faces training will be associated with baseline irritability. For those in the active condition, linear regression will test the association between pre-training ARI (irritability) and learning rate to reversal feedback of baseline angry judgments to the two ambiguous morphs.

Hypotheses 2.2 and 2.3: Active, but not sham, IBT will evoke greater neural response in threat-learning systems. For each person, learning will be modeled with regressors coding the “value” or trialwise likelihood that a participant considers the morph to be angry. The amplitude of BOLD %signal change (activity) or amygdala covariance (generalized psychophysiological interaction; connectivity) related to these regressors represents neural response to value. Critically, these regressors represent learning itself where value is changing towards benign judgments in the active training condition to two ambiguous morphs. These will be carried forward to the second level mixed-effects linear models of the effects of morph by pre-training ARI by training condition. A voxel-wise threshold of  $p < .001$ , whole-brain, cluster corrected to  $p < .05$  via permutation testing or Monte Carlo simulation as appropriate, will be used to identify significant associations. A three-way interaction of change in value by morph by training condition will indicate neural areas where learning is influenced by irritability in active but not sham training of reversals of ambiguous morphs. In addition, our *a priori* identification of the likely role of the amygdala, OFC, and ACC justifies follow-up region-of-interest analyses of mean activity or connectivity extracted from these areas with the same omnibus mixed-effects model.

Exploratory Hypothesis 3.1: Change in irritability after training is associated with change in hostile interpretation bias. We will investigate this relationship with mixed-effects linear models with ARI (irritability), balance-point (interpretation bias), and time of assessment (pre- or post-training) as within-person variables.

Exploratory Hypothesis 3.2: Change in irritability after training is associated with magnitude of neural threat-learning system response. We will investigate this relationship with mixed-effects linear models with ARI (irritability), mean value-associated connectivity or activity in the amygdala, OFC, and ACC, and time of assessment (pre- or post-training) as within-person variables.

As requested by NIMH scientific review, I will conduct two additional, secondary analyses: 1) a mediation analysis of active IBT on change in irritability and 2) a multivariate analysis of the shared and unique effects of irritability, anxiety, and depression on hostile interpretation bias.

Power analysis. For Aim 1, a sample size of 100 achieves 80% power to detect an effect size of the expected association of at least  $r = .25$  between baseline hostile interpretation bias and baseline irritability using Pearson correlation at a one-tailed alpha of .05. Thus, the proposed study will have sufficient power to detect small to medium sized interaction effects. The study is overpowered for detecting expected effects of IBT on hostile interpretation bias which should be large. For Aim 2, a sample size of 100 likewise achieves more than 80% power to detect the expected large association between baseline irritability and learning. For imaging, using a medium effect size of a term in a general linear model ( $R^2 = .15$ ), the required sample for 80% power is 50 individuals ( $p = .05$ ). Our previous study that examined IBT-related changes to face-emotions was medium to large in the orbitofrontal cortex. Thus, the proposed study will have sufficient power to detect small to medium sized interaction effects. Aim 3 is exploratory; this study may estimate effect sizes for future research.

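### Entered as main effects, the plan's covariates do not adjust the within-person terms tested in H2.2/2.3 and H1.2; for H2.2/2.3 this leaves anxiety and depression uncontrolled

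*Combined protocol and SAP*

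**What the plan says.** All of this is in section F, Data Analysis Plan.

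- **Adjustment rule (Hypothesis Testing).** Sex, age, SES and IQ are minimisation factors. The plan then adds: "Additional potential factors are anxiety, depression, pubertal development, and in- or out-of-scanner training". The rule has two triggers. One is imbalance: "If an imbalance across training groups occurs in any of these factors". The other is a significant association between a factor and an independent variable. In either case "it will be entered into the omnibus model as a covariate". No covariate-by-time, covariate-by-morph or covariate-by-condition term appears anywhere in the section.
- **H1.2.** A mixed model of balance point with "training condition (active vs. sham), and time of interpretation bias assessment (pre- or post-training) as independent variables of interest". The model also has a random intercept for each participant. The condition x time product is not written out, but the hypothesis (active but not sham training reduces bias) requires it.
- **H2.2/2.3.** Person-level neural estimates go into "second level mixed-effects linear models of the effects of morph by pre-training ARI by training condition".
- **H1.1 and H2.1.** Ordinary regressions with one outcome value per person.

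**The concern.** Every listed factor has one value per person if baseline scores are used. The terms tested in H1.2 and H2.2/2.3 are within-person contrasts (post minus pre; one morph against another) compared across people. A quantity that is constant within a person cancels from such a contrast. A reader who sees anxiety in the model would take the tested term as adjusted for anxiety when it is not.

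This matters most in H2.2/2.3. Training condition is randomised but ARI is not. The Background (IBT to Treat Irritability) says irritability has concurrent associations with anxiety and depression. ARI is an independent variable, so the second trigger is likely to apply to them. The rule would then name the right confounders and leave the tested term as it was. Minimisation does not help, because it balances arms and cannot separate ARI from its correlates. The added secondary analysis of irritability, anxiety and depression concerns hostile interpretation bias, not neural response.

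**Working it through.** **The plan's own figures.** The plan gives no figure for this point. Its power statements reproduce and are not in dispute. For r = .25, one-tailed alpha .05, n = ((1.645 + 0.842)/atanh(.25))² + 3 = 98, and N = 100 gives 80.8% power. For an imaging term with R² = .15, about 47 people are needed and 50 give about 83%.

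**Step 1: algebra.** For person i at occasion t in H1.2, with covariate x_i as a main effect:

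y_it = a + b·cond_i + c·t + d·cond_i·t + g·x_i + u_i + e_it

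Subtracting pre from post gives c + d·cond_i + (e_i1 - e_i0). Both g·x_i and u_i are gone, so x_i cannot alter d. If x_i also predicts change (a term h·x_i·t), then h·x_i stays in the difference, and only a covariate x time term removes it. The same holds for a contrast between morphs.

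**Step 2: numerical check.** REML random-intercept models on simulated complete data, with the true tested effect set to zero. The imbalance, slopes and correlation are assumptions; the equality of the first two result columns does not depend on them.

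| Term | No covariate | Covariate as main effect | With matching interaction |
|---|---|---|---|
| Condition x time (50 v 50; imbalance 0.5 SD, covariate slope on change 0.5; mean of 200 runs) | 0.221 | 0.221 | -0.015 |
| Morph x ARI x condition (25 v 25; covariate-ARI correlation .5; mean of 100 runs) | 0.262 | 0.262 | 0.008 |

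The largest difference between the first two columns in any run was 1.3e-14 and 1.0e-15 respectively. In the data sets inspected, standard errors agreed to about 1e-6. The main effects did move (in one data set, condition in the H1.2 model went from 0.629 to 0.053).

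**Step 3: conditions on the equality.**
- Missing data: with 10 of 100 post scores missing, condition x time moved by 0.014 on average (maximum 0.051), and the bias stayed (0.250 to 0.249).
- Time-varying covariates: anxiety or depression entered as repeated scores would change the estimate (one run: 0.136 to 0.172).
- Random structure: a random person intercept. The plan states a person effect for H1.2; for H2.2/2.3 it is assumed here.

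**Step 4: where the rule works.** In a simulated H1.1-type regression with a confounder and no true association, the slope went from 0.200 to 0.002 when the covariate was added.

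**Step 5: size in H2.2/2.3.** Inputs: n = 50 (the plan's imaging sample), no ARI effect, two-sided 5% single test. The ARI-anxiety correlation r and the share R² of contrast variance due to anxiety x condition are assumptions; the documents give neither.

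| R² | r = .3 | r = .5 | r = .6 |
|---|---|---|---|
| .15 | 11-13% | 25-27% | 34-36% |
| .05 | 8% | 11% | 14-15% |
| .02 | 6% | 8% | 8% |

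Ranges reflect separate simulation runs. As a rough check, the ARI x condition test has noncentrality √n·r·√R²/√(1 - r²R²). For r = .5 and R² = .15 this is 7.07 x .5 x .387/√(1 - .0375) = 1.40, a rejection rate of about 28% on 46 df. For R² = .05 it is 7.07 x .5 x .224/√(1 - .0125) = 0.80, about 12%. With the covariate's interaction in the model, the simulated rate at R² = .15 was about 4-6%.

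**Step 6: size in H1.2.** With 50 per arm, a 0.4 SD imbalance and a covariate effect of 0.5 on change, the expected bias is 0.4 x 0.5 = 0.20. Simulated with a true effect of 0.5, the estimate was 0.757 (SE 0.177) both without the covariate and with its main effect, and 0.562 (SE 0.147) with covariate x time. The SE of an imbalance is √(2/50) = 0.20 SD, so 0.4 SD is a 2-SE event. Averaged over randomisations, the type I error of the unadjusted test was 5.0% in simulation.

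**The case against.** **The text does not exclude interactions.** True. Main-effect entry is the ordinary reading, not a stated one. But the section specifies no interaction, so an analyst who follows it as written gets the unadjusted term, and clarification is needed either way.

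**H1.2 is already protected.** This stands. A reader might infer that the H1.2 result would be biased or its test invalid. The documents do not support that: training is randomised, minimisation covers sex, age, SES and IQ, and the 2 x 2 design with 25 acceptable participants per arm balances scanner setting. A covariate that affects only the level of balance point is removed by the pre/post contrast itself. In the Step 6 example both estimates are clearly significant, and the plan expects a large training effect.

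**The H2.2/2.3 rates are assumption-driven.** Also fair. Setting anxiety x condition at 15% makes the confounder as large as the effect the plan is powered for. The three-way term is confounded only if the anxiety effect on the morph contrast differs between arms. If that effect exists only in the active arm, the rates become 8%, 15% and 22% for r = .3, .5 and .6. The whole-brain rule is voxel-wise p < .001 with cluster correction, so a nominal 5% rate applies only to tests of the region-of-interest type. A reader might infer that an irritability finding here would be an artefact; the documents show only that the plan could not rule it out.

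**The safeguard is not useless.** Correct: it works for H1.1, H2.1 and the post-training-only comparisons.

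**Conclusion.** The point holds for two analyses and matters for one. On the main-effect reading, with person-level covariates, complete within-person data and a random person intercept, the adjustment rule leaves the tested terms in H2.2/2.3 and H1.2 unchanged. Accrual to acceptable data (Randomization section) should largely secure completeness; modest missingness moves the estimate slightly without removing the bias.

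In H2.2/2.3 the likely confounders are named by the protocol itself, and the rule is likely to trigger for them. At n = 50 a significant ARI-anxiety correlation would appear in about 56% of samples if r = .3 and 96% if r = .5. The resulting single-test error is about 11-35% or 8-15%, depending on whether the confounder explains 15% or 5% of the contrast, and close to nominal at 2%. In H1.2 the loss is precision and protection against chance imbalance in predictors of change.

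Should-fix. A must-fix rating would need either an invalid H1.2 test or a documented size for the anxiety or depression effect, and the documents show neither.

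**What to change.** Add to Hypothesis Testing in section F:

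- **H2.2/2.3.** A triggered covariate, chiefly baseline anxiety and depression, enters as covariate x morph x condition with all lower-order terms. Equivalently, reduce each person to the tested morph contrast and regress it on condition, ARI, ARI x condition, covariate and covariate x condition.
- **H1.2.** A triggered covariate enters as covariate x time.
- State that covariates are baseline values, and write the condition x time term into H1.2. For H2.2/2.3, reconcile the two descriptions of the three-way term: one contains ARI, the other change in value.

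No new data are needed. In the contrast form of H2.2/2.3, each covariate costs about two residual degrees of freedom. With 50 people and four base parameters (intercept, condition, ARI, ARI x condition), 50 - 4 = 46 remain. All seven non-scanner factors would take 14 and leave 32, so restrict this to the covariates that are triggered.
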